## 6.4.1 Economic analyses

This will be an incremental cost-effectiveness analysis of the EC intervention with passive UC intervention in comparison to the active UC intervention. There are three main components of data collection for the cost-effectiveness analysis.

Firstly, the costs of providing the EC intervention will be recorded and includes the costs of staff training, staff time for intervention delivery (including overheads), and of the EC products provided. We will collect costs prospectively alongside the cRCT in monetary form for direct expenses, and in terms of quantities for resources and apply local unit costs to the quantities of each resource utilised. We will also record the costs of providing UC.

Secondly, following NICE guidance (21), health care utilisation data will be collected. We will record health care utilisation data for contacts with the NHS and personal and social services (PSS) using a bespoke service use questionnaire which will incorporate revisions informed by the data from the feasibility study. This includes the use of primary and secondary health care services and social care. Quantities recorded are multiplied by national average unit costs (22,23) to derive a cost profile for each patient in each arm of the trial. The service use questionnaire will also include brief questions on patient's out of pocket expenditure on cessation aids, costs of travel to health services and lost productivity.

Thirdly, EQ-5D-5L (24) will be administered at each follow up. The EQ-5D-5L responses will be used to derive utility values and Quality Adjusted Life Years (QALYs) will be then calculated with these utility values using the area under the curve approach (25) based on a linear change between observations. The validity of the current EQ-5D-5L UK population tariff has been challenged and will therefore use the methodology recommended by NICE at the time of analysis to calculate QALYs which will be the primary outcome for the economic evaluation (23,25).

Intervention and health care costs are combined with QALYs to estimate the incremental cost per QALY of the EC intervention with passive UC comparing to active UC intervention at the primary endpoint from an NHS/PSS perspective. Underlying uncertainty around the decision to adopt the intervention is assessed using non-parametric bootstrap re-sampling. Bootstrapping is an efficient

method for calculating the confidence limits for the incremental cost-effectiveness ratio (ICER) as its validity does not depend on any specific form of underlying distribution. We will perform the bootstrap 5000 replications and construct the 95% confidence intervals for the ICERs based on the bootstrapping results. Cost-effectiveness acceptability curves (CEACs) will be constructed based on the bootstrap iterations (27) to estimate the probability that the intervention is cost-effective at different threshold values for one QALY. We will also present a secondary analysis using the cost per quitter at the primary endpoint from an NHS and PSS perspective and a societal perspective (including patient cost of buying cessation aids, travel and productivity).

In addition to addressing the uncertainty surrounding the point estimate of the ICER, sensitivity analysis is undertaken to assess the effect of missing data. In the main analysis, missing data will be imputed using Rubin's multiple imputation method (28). As part of the sensitivity analysis, we will conduct a complete case analysis (CCA) whereby results are analysed only for those participants who had both the completed cost and outcome data at the same time. The missing at random assumption for multiple imputation will also be assessed using the methods recommended by Faria and colleagues (29).

The cost-effectiveness analysis will further use an existing model, with adaptations, to extrapolate the longer-term cost-effectiveness (26). The model is a three-state Markov model: former smoker, current smoker and death and was originally constructed for an SMI population. It takes into account age, gender, lifetime relapse rate, incidence of smoking-related diseases and their smoking-attributable costs, and QALYs. The basic model assumptions are generic and fit all populations. The model parameters could be adapted to fit other populations if required and we will adapt the model to fit the trial population based on evidence available (30). Trial data is combined with secondary data to estimate lifetime QALYs and cost per QALY gained from the NHS/PSS perspective as per NICE guidance and will therefore only use NHS and PSS costs and will not incorporate patient costs which are not relevant to this perspective. Uncertainties will be assessed using probabilistic sensitivity analysis and presented in the form of CEACs.

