## 2.2 Trial Design

Multi-centre two-arm cluster randomised controlled trial with mixed-method embedded process evaluation and economic evaluation.

A 6-month internal pilot with the first 120 participants (8 centres) is included to monitor recruitment within the given timeframe. The following stop/go criteria are specified: 90% recruitment achieved = go. Amber: 60-90% recruitment achieved = present action plan to Trial Steering Committee (TSC) with strategies for overcoming identified recruitment barriers. TSC to manage this plan with involvement of the study funder, and formally assess recruitment again at 12 months. Red: <60% = Rescue plan considered by TSC and funder; joint decision on whether the study should continue.

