## 4.3 Randomisation Procedures

Centres will be randomised (1:1 in permuted blocks), allocated to the EC intervention (n=16) or Usual Care (n=16) using permuted block randomisation to ensure balance. Where possible, staff at centres will obtain expressions of interest (EOI) from potential participants who meet the inclusion criteria before the centres receive training and are made aware of their allocated condition. Researchers will approach the first 15 who have expressed an interest in the study and invite them to a baseline session where informed consent will be taken. This approach is preferred over randomly selecting participants from the EOI list to reduce disharmony among clients attending centres. Our final sample size allows us to retain 90% if we under or over-recruit by +/- 3 in each centre (see section 6.3). The intervention the participant receives will be based on their centre's allocation. The trial statistician will create the randomisation list, which will be embedded/read in REDCap, which will be hosted by Kings College London (KCL).

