## 6.3 Sample Size

Our sample size is based on our feasibility trial. For, 0.05 alpha (two-tailed), 90% power, and cluster size of 15 participants (the feasibility study average in day centres (5)), this trial requires 240 participants per arm and 16 clusters per arm (480 participants and 32 clusters in total) to detect a difference of 5.75 between arms (i.e. 6.25% vs 0.5% respectively in the EC vs UC arms). The intraclass correlation coefficient (ICC) was set at 0.01 assuming equal cluster sizes. A final sample of 480 provides 90% power if the cluster size was smaller (n = 12) or greater (n=18) than the planned 15 participants per cluster.

There is sufficient power to detect more modest differences with smaller cessation rates in the EC arm; for example, with 5% cessation rate in the EC arm (vs. 0.5% UC), allowing 81% power with an ICC of 0.01 and 74% with an ICC of 0.025.

Sensitivity sample size calculations were conducted for the secondary outcome measuring 50% CO reduction, as previous studies have shown that CO reduction is a good predictor of future successful smoking quit attempts (20). If we assumed a minimally clinical important difference (MCID) to be 10% (i.e. 13% EC vs. 3% NRT), for 90% power, ICC = 0.01, alpha = 0.05 (two-tailed) and cluster size 15, we would need 360 participants across 24 clusters in total.

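### The 95% CI planned for the cost-per-QALY ratio is likely to be uninterpretable at 24 weeks, and the economic section makes no stated provision for centre clustering

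*Protocol*

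**What the plan says.** Only the protocol is available. On the economic evaluation, section 6.4.1 states: "Underlying uncertainty around the decision to adopt the intervention is assessed using non-parametric bootstrap re-sampling". It continues: "We will perform the bootstrap 5000 replications and construct the 95% confidence intervals for the ICERs based on the bootstrapping results". The reason given is that bootstrap validity does not rest on any particular underlying distribution. Cost-effectiveness acceptability curves are to be built from the same replicates. A secondary analysis reports cost per quitter, and a longer-term Markov model is handled by probabilistic sensitivity analysis with acceptability curves.

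Section 6.4.1 does not name the resampling unit, the type of bootstrap interval, or a rule for replicates with a zero or negative QALY difference. It does not mention net benefit, states no threshold values, and gives no centre level for the multiple imputation.

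Elsewhere the centre is central. The design is a "Multi-centre two-arm cluster randomised controlled trial with mixed-method embedded process evaluation and economic evaluation" (section 2.2), with centres "allocated to the EC intervention (n=16) or Usual Care (n=16) using permuted block randomisation to ensure balance" (section 4.3). The sample size allows for clustering: "The intraclass correlation coefficient (ICC) was set at 0.01 assuming equal cluster sizes" (section 6.3). The primary analysis has random effects for clusters (section 6.4). Section 6.2 sets the horizon of the within-trial economic analysis at 24 weeks.

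**The concern.** There are two separate matters, and the first is the stronger.

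**The ratio interval.** A negative ICER can mean that the intervention is cheaper and better, or that it is dearer and worse. When bootstrap QALY differences fall on both sides of zero, sorting the ratios mixes these opposite results, and the ratio jumps between very large positive and negative values as the denominator passes through zero. Freedom from distributional assumptions does not cure this. The protocol fixes the interval, the number of replicates and the justification, so this is a stated choice.

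**Clustering.** A bootstrap needs independent resampling units. Here the randomised unit is the centre, and section 6.4.1 does not say that centres are resampled. Some costs plausibly vary by centre: staff are trained centre by centre (section 4.4), staff delivery time and local unit costs enter the intervention cost (section 6.4.1), and stop smoking services are said to differ widely (section 4.4).

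Cost-effectiveness is part of the first research question (section 1.3), and QALYs are the primary economic outcome. At stake are one headline interval that could not be read, and possibly intervals and acceptability curves that are too precise.

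**Working it through.** **1. The plan's own clustered sample size.** Inputs from section 6.3: "0.05 alpha (two-tailed), 90% power, and cluster size of 15 participants"; "6.25% vs 0.5% respectively in the EC vs UC arms"; ICC 0.01.
- The two-proportion formula gives 206 per arm without clustering.
- Design effect = 1 + (15 − 1) × 0.01 = 1.14.
- 206 × 1.14 = 235; 235 / 15 = 15.7, rounded up to 16 centres, that is 240 per arm.

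This reproduces the plan. Power at a 5% EC quit rate comes to 81% (ICC 0.01) and 74% (ICC 0.025), also as stated. So the plan itself treats clustering as material.

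**2. Expected QALY difference through quitting.** The documents give no utility gain per quitter; I assume 0.02 to 0.10. Gain = 0.0575 × utility gain × 24/52.
- At 0.02: 0.0575 × 0.02 × 0.4615 = 0.0005.
- At 0.10: 0.0575 × 0.10 × 0.4615 = 0.0027.

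This credits each extra quitter with the gain for the whole 24 weeks, and counts nothing for smoking reduction.

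**3. Standard error of the QALY difference.** The SD is not given; I assume a 24-week QALY SD of 0.05 to 0.12, with 240 per arm and before clustering. SE = SD × √(2/240).
- SD 0.05: 0.0046.
- SD 0.12: 0.0110.

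**4. Share of replicates with a negative QALY difference.** Φ(−gain / SE):

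| 24-week QALY SD | utility gain 0.02 | 0.05 | 0.10 |
|---|---|---|---|
| 0.05 | 45% | 39% | 28% |
| 0.08 | 47% | 43% | 36% |
| 0.12 | 48% | 45% | 40% |

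The range is 28% to 48%. Clustering would widen the SE and move these shares closer to one half.

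**5. What the ratio limits look like.** Illustrative case: QALY gain 0.0025, SD 0.12, cost difference 100, cost SD 1500, costs and QALYs independent.
- P(QALY difference > 0) = Φ(0.0025 / 0.01095) = 0.590.
- P(cost difference > 0) = Φ(100 / 136.9) = 0.767.
- Dearer and better: 0.590 × 0.767 = 45%. Dearer and worse: 0.410 × 0.767 = 31%. Cheaper and worse: 0.410 × 0.233 = 10%. Cheaper and better: 0.590 × 0.233 = 14%.

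In 5000 draws, the 2.5th and 97.5th percentiles of the ratio were about −184,000 and +180,000; another set gave about −195,000 and +193,000. The probability of being cost-effective at an illustrative threshold of 20,000 stays well defined, at about 0.43.

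**6. How large a gain would rescue the interval.** In the same illustration the interval becomes usable at roughly 3 SE from zero. Even with the smallest SD, 3 × 0.0046 = 0.0137 QALYs, which needs a utility gain per quitter of 0.0137 / (0.0575 × 24/52) = 0.52. That is about five times the top of the assumed range.

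**7. Clustering, if participants were resampled singly.** True SE / reported SE = √(1 + 14 × ICC); coverage of a nominal 95% interval = 2Φ(1.96 / ratio) − 1.

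| ICC | ratio | coverage |
|---|---|---|
| 0.01 | 1.07 | 93% |
| 0.025 | 1.16 | 91% |
| 0.05 (assumed) | 1.30 | 87% |
| 0.10 (assumed) | 1.55 | 79% |

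The first two ICCs stand in section 6.3, but for abstinence. The documents give none for costs or QALYs. A simulation of 16 centres of 15 per arm gave 92%, 87% and 77% for individual resampling at ICC 0.01, 0.05 and 0.10, and 93%, 91% and 94% for whole-centre resampling.

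**8. Which cluster bootstrap.** Drawing centres and then participants, without correction, counts within-centre variance twice. At ICC 0.01 and unit variance, the true variance of a centre mean is 0.01 + 0.99/15 = 0.076. The uncorrected two-stage value is 0.076 × 15/16 + 0.99 × (14/15)/15 = 0.133. The SE ratio is √(0.133 / 0.076) = 1.32, too large by a third. Whole-centre resampling gives √(15/16) = 0.97, and simulation gave 0.96.

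**The case against.** **A reader might infer that the plan ignores clustering and takes percentile limits.** The protocol says neither. Resampling whole centres is also a non-parametric bootstrap, the interval type is not given, and such details may properly sit in an analysis plan that is not shown. This objection stands: the most that can be said is that section 6.4.1 states no provision for centres. At the planning ICC of 0.01 the effect is small. The larger losses in the table need ICCs that the documents do not supply. Health-care quantities are also priced at national average unit costs, which removes price differences between centres, though not differences in use.

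**A reader might also infer that the whole economic uncertainty analysis is uninterpretable.** It is not. The acceptability curves stay defined in every quadrant, and the longer-term model plans no ratio interval. For cost per quitter, the denominator under the design assumptions lies 5.75 / 1.74 = 3.3 SE from zero, where 1.74 points is √[(0.0625 × 0.9375 + 0.005 × 0.995) × 1.14 / 240]. A ratio interval is usable there.

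**The QALY figures are assumed.** That is true, and benefit from smoking reduction is left out. Even so, the required gain in step 6 is far outside the assumed range.

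None of this rescues the 95% interval for cost per QALY, which the protocol does fix.

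**Conclusion.** The point holds in two parts of unequal strength.

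The commitment to a 95% confidence interval for the cost-per-QALY ratio is a poor choice for this trial, and the stated justification does not support it. The conclusion rests on the assumed utility gain and QALY SD, but holds throughout the ranges shown. It concerns one reported interval and not the acceptability curves.

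The absence of any stated centre level in the economic bootstrap and imputation is a gap in the text, not a demonstrated error. If participants were resampled singly, nominal 95% intervals would cover about 93% at ICC 0.01 and 91% at 0.025, and less if costs or QALYs cluster more strongly. The acceptability curves would then also be too precise.

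Both should be settled before analysis, because a method chosen after the replicates are seen would be post hoc.

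**What to change.** In section 6.4.1 and the health-economic plan:

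- Replace the 95% CI for the cost-per-QALY ICER with incremental net monetary benefit and its 95% CI. Name the thresholds in advance, since the protocol states none. Show it with the cost-effectiveness plane and the acceptability curve.
- Draw replicates by resampling whole centres within arm. Acceptable alternatives are a two-stage bootstrap with shrinkage correction, or a bivariate cost and QALY model with centre random effects. Do not use an uncorrected two-stage bootstrap.
- Make the multiple imputation respect centres.
- Adjust the QALY difference for baseline EQ-5D, which is already collected.

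No new data are needed. The cost is a few lines of text, slightly more programming and somewhat wider intervals.

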#### 6.4.2 Process evaluation

The process evaluation will use both quantitative and qualitative approaches to explore treatment context, fidelity of implementation, mechanisms of change and sustainability. Methods include observation, checklists, staff evaluation forms, questions within participant baseline and follow-up questionnaires, in-depth qualitative interviews, and decision maker workshops.

16 members of staff, purposively sampled from 8 centres (4 in England, 2 in Scotland and 2 in Wales) will be recruited for process evaluation interviews.

## 7 Data Handling & Record Keeping

## 7.1 Confidentiality

Only study personnel will have access to study data. We will not request any patient identifiable data or medical information about participants from their other doctors (hospital or general practitioner, GP).

All information will be kept confidential. After the study appointment, the researcher will upload all data (excluding personal data) onto REDCAP. Copies of all documents regarding the study will be kept in the trial master file (TMF) and/or relevant site file. Participants will be assigned a trial ID number.

## 7.2 Study Documents

[figure not shown]
- A signed protocol and any subsequent amendments
- Current/Superseded Participant Information Sheets (as applicable)
- Current/Superseded Consent Forms (as applicable)
- Current/Superseded Debrief Forms
- Study Advertisements
- Indemnity documentation from sponsor
- · Conditions of Sponsorship from sponsor
- Contract with the NIHR
- Collaboration Agreement
- Documentation relating to adoption into the CRN portfolio
- · Ethics submissions/approvals/correspondence
- CVs of PIs, TM, AL and RAs
- GCP certificates
- Schedule of responsibilities / delegation log
- Data flows
- · Participant identification log
- Screening log
- Enrolment log
- Risk Assessments
- Current/Superseded Logic Model
- Correspondence relating to the trial

## 7.3 Case Report Form

[figure not shown]
Trained research assistants in each area will be responsible for ensuring the correct sections are completed at the relevant time-points throughout the study. All completed CRFs will be reviewed and signed off by the area leads

## 7.4 Record Retention and Archiving

All information relevant to the study will be archived and retained for at least 10 years at London South Bank University (unless otherwise specified). Consent forms, paper CRFs and participant contact details files will be kept securely at study sites until the end of the study and then transferred securely to LSBU. Participants contact details (personal details) will be kept securely for 2 years from the end of the study (see Figs. 2 & 3 data flows). Electronic data (which will not include participants' personal data) will be kept on a secure online database at LSBU and made freely available on openresearch.lsbu.ac.uk for at least 20 years. The sponsor will be informed in writing when and where all data is archived.

SCeTCH protocol Version 1.1 25 January 2022

## 7.5 Compliance

The TM, CI and area leads will ensure that the trial is conducted in compliance with the principles of the Declaration of Helsinki (1996), and in accordance with all applicable regulatory requirements including but not limited to the Research Governance Framework, sponsor's policies and procedures and any subsequent amendments.

## 7.6 Clinical Governance Issues

#### 7.6.1 Ethical Considerations

This protocol and any subsequent amendments, along with any accompanying material provided to the participant in addition to any advertising material will be submitted by the Principal investigator to the Research Ethics Committee/Research and Enterprise Management System (HAPLO).

## 7.7 Quality Control and Quality Assurance

#### 7.7.1 Risk Assessment

The study will be risk assessed by the PIs/TM and signed off by the LSBU Health, Safety and Resilience (HSR) Team in accordance with LSBUs Health and Safety Policy. In addition, each homeless centre site will be risk assessed by the area leads using the standard LSBU risk assessment template before recruitment begins at that centre. These risk assessment documents will be signed off by the TM and a copy of all risk assessment documents will be kept in the TMF.

#### 7.7.2 Study Monitoring

Records relating to participant consent, recruitment and follow up will be kept on REDCap. Monthly recruitment and follow up figures will be kept in the TMF and reported to the NIHR via the NETSCC-MIS by the TM. Data from CRFs entered in REDCap will be monitored by area leads who will be responsible for checking 10% of the entries in their area. An interim report at the end of the pilot study will be produced for the TSC and funder who will review recruitment and follow up figures against the study stop/go criteria and advise on progression of the trial.

**Table 2: Stop-Go Progression Criteria** 

Recruitment	Criteria	Action
90%	Go	Continue with trial
60-90%	Amber	Action plan to TSC & funder and formally reassess recruitment again at 12 months
<60%	Rescue Plan*	Rescue plan considered by TSC and funder and decide whether to continue

## 7.8 Audit and inspection

The investigator will permit study-related monitoring, audits, and inspections by the Ethics Committee, the sponsor, government regulatory bodies of all study related documents (e.g., source documents, regulatory documents, data collection instruments, study data etc.).

## 7.9 Reporting of Serious breaches in GCP or trial protocol

All breaches and potential breaches in GCP or trial protocol will be logged by the area leads and reported to the PI or TM within 24 hours. The PI/TM will be responsible for reporting these to the REC/sponsor and the NIHR (via the incident reporting form) within 24 hours of becoming aware of the event.

## 7.10 Trial Committees

A Trial Steering Committee (TSC) and a Data Monitoring Committee (DMC) will be convened. The TSC will meet twice per year, the DMC once per year. A Trial Management Group (TMG) comprising the CIs, TM and area leads will meet monthly to communicate and monitor progress of the trial and address any problems arising.

## 7.11 Publication Policy

Study results will be written up for submission to international conferences and peer reviewed journals. No participant will be identifiable from any publication or report. We will also provide public and participant lay outputs.

